## Clinical Investigation Plan

### 5.5 Study Flow Chart

The Study Flow Chart (Figure 1) and Table 2 below summarize subject flow and visit requirements for this clinical study.

Figure 1: Study Flow Chart

## Clinical Investigation Plan

Table 2: List of Tests and Procedures

Visit	Baseline	Intervention (Implant within 30 days of consent)	Pre-discharge (Discharge or 7 days post-implant, whichever is sooner)	6 Month (+/- 30 days)	1 Year Follow-Up (+/- 60 days)	2 Year Follow-Up (+/- 60 days)	3 Year Follow-Up (+/- 60 days)	4 Year Follow-Up (+/- 60 days)	5 Year Follow-Up (+/- 60 days)
Study Activity									
Patient Eligibility	X								
Informed Consent Process	X								
Demographics	X								
Physical Examination	X								
Cardiovascular History	X								
Current Cardiac Medications	X								
Medical History	X								
NYHA	X			X	(X)	(X)	X	(X)	X
STS and EuroSCORE II	X								
Serum Creatinine	X								
Echo	(X)	(X)	X	X	(X)	(X)	X	(X)	X
Aortic Valve Replacement Information		X							
Operation Information		X							
Adverse Event		(X)	(X)	(X)	(X)	(X)	(X)	(X)	(X)
Cardiac Medication Assessment			X	X	X	X	X	X	X

(X) If applicable

## Clinical Investigation Plan

### 5.6 Description of Activities Performed by Sponsor Representatives

Trained Sponsor personnel may provide technical expertise and technical guidance on the use of the Trifecta GT device. This may include training and case coverage.

While Sponsor representatives may perform these activities, the Principal Investigator remains responsible for ensuring all clinical study data are collected as required per CIP.

### 5.7 Subject Study Completion

Subject participation in the clinical study will conclude upon completion of the 5 year visit. Upon completion of subject participation in the clinical study, the subject will return to standard of care.

### 5.8 Subject Withdrawal or Discontinuation

Subjects must be informed about their right to withdraw from the clinical study at any time and for any reason without sanction, penalty or loss of benefits to which the subject is otherwise entitled. Withdrawal from the clinical study will not jeopardize their future medical care or relationship with the investigator. Subjects will be requested to specify the reason for the request to withdraw, however a response is not required. The investigator must make all reasonable efforts to retain the subject in the clinical study until completion of the clinical study.

Reasons for subject's withdrawal include, but are not limited to:

- Subject refuses to continue participating in the study
- Subject is deceased (cause must be documented)
- Subject has a failed Trifecta GT valve implantation attempt (30 day AE collection period required)
- Subject has Trifecta GT valve explanted
- Subject is lost to follow-up: A subject will be considered 'Lost to Follow-up' after two missed visit(s) and a minimum of two unsuccessful phone calls from study site personnel to the subject or contact to schedule the next follow-up visit. These two phone calls must be documented in the subject's hospital records. If the subject is deemed lost to follow-up, a letter identifying the subject's date of withdrawal from the study should be sent to the subject's last known address or to the subject's general practitioner (GP) and a copy of the letter must be maintained in the subject's hospital records.

If a subject withdraws from the clinical study, the site will record the subject's reason for withdrawal, on a Withdrawal Form. When subject withdrawal from the clinical study is due to an adverse event, the subject will be followed by the site until resolution of that adverse event or determination that the subject's condition is stable. The status of the subject's condition should be documented at the time of withdrawal.

In case of subject withdrawal, the site should make attempts to schedule the subject for a final study visit. At this final study visit, the subject will undergo the following assessments:

- Adverse event collection (if applicable)

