#### 5.4.2 Intervention

Subjects will undergo a Trifecta GT valve implantation surgery. If the implant procedure is attempted but the Trifecta GT valve is not implanted, the subject will be withdrawn from the study after a 30-day adverse

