### 5.4.4 Scheduled Follow-ups (6 Months and Annually Through 5 Years)

Scheduled study follow-ups should occur at the participating institution. If an office visit is not possible, follow-up may occur via a telephone call with the subject for years 1, 2 and 4. The following information will be collected at each follow-up visit.

[figure not shown]
- NYHA class (not required for telephone visits)
- Cardiac medications
- Echo (required at 6 months, 3 years and 5 years including delivery to core laboratory)
- Adverse events (if applicable)
- Death (if applicable)

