### 8.2 Safety Reporting

Safety surveillance and the safety reporting by the investigator starts as soon as the subject is enrolled in this clinical study. Refer to Section 5.3 for the definition of subject enrollment.

The safety surveillance and the safety reporting will continue until the last study visit has been performed, the subject is deceased, the subject/investigator concludes his participation into the clinical study or the subject withdrawal from the clinical study.

The PI will report the event to the IRB/EC per their reporting requirements. The following are reportable events per this CIP (see Appendix B for definitions):

- Adverse Device Effects (regardless of seriousness)
- Serious Adverse Events (regardless of severity) including those specified in Edmunds Criteria which include:
  - Structural valve deterioration

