## Clinical Investigation Plan

- Nonstructural dysfunction
- Embolism (valve related)
- Valve thrombosis
- Major bleeding event
- Endocarditis
- Death

The above events will be reported to the Sponsor. The Sponsor will ensure that all events are reported to the relevant authorities as per regulations. The sites should notify the Sponsor of reportable adverse events by creating and saving the applicable CRF within the electronic data capture (EDC) system.

The investigator should report all SAEs to the Sponsor as soon as possible but no later than outlined below.

Clinical Site	Reporting timelines
All Sites	SAEs must be reported to the Sponsor no later than 3 calendar days from the day the study personnel became aware of the event or as per the investigative site's local requirements, if the requirement is more stringent than those outlined.

The date the study staff became aware the event met the criteria of an SAE must be recorded in the source document. The Investigator will further report the SAE to the local IRB/EC according to the institution's IRB/EC reporting requirements.

Adverse events will be monitored until they are adequately resolved or the subject has ended his/her participation in the trial, whichever comes first. The status of the subject's condition should be documented at each visit.

Records relating to the subject's subsequent medical course must be maintained and submitted (as applicable) to the Sponsor until the event has subsided or, in case of permanent impairment, until the event stabilizes and the overall clinical outcome has been ascertained. Adverse events will be monitored until they are adequately resolved. The status of the subject's condition should be documented at each visit.

The following information should be collected for each event:

- Date AE occurred
- Date the site, PI, became aware of the event
- Main symptoms of the event
- Treatment
- Seriousness
- Relationship to device
- Resolution status

Additional information may be requested, when required, by the Sponsor in order to support the reporting of AEs to regulatory authorities.

The PI must notify the IRB/EC, if appropriate, in accordance with national and local laws and regulations, of the AEs reported to the Sponsor.

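### Explant is a listed withdrawal reason and no readable text asks for vital status afterwards, so where a site withdraws an explanted subject, later deaths may be missing from 5-year all-cause mortality

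*Protocol*

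**What the plan says.** **Endpoint.** Protocol 4.3.2 and 6.1.2 and SAP 1.4.2 set all-cause mortality as a descriptive endpoint at 5 years after implant, with no restriction to time with the study valve in place. Valve-related mortality has the same horizon.

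**Withdrawal.** Protocol 5.8 includes "Subject has Trifecta GT valve explanted" in its list of withdrawal reasons. The same section says "The investigator must make all reasonable efforts to retain the subject in the clinical study until completion of the clinical study". By contrast, Protocol 5.4.2 does direct withdrawal after a failed implant: "the subject will be withdrawn from the study after a 30-day adverse" event collection period.

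**After withdrawal.** Protocol 5.8 asks for an attempted final visit whose only listed content is adverse event collection. If an adverse event caused the withdrawal, "the subject will be followed by the site until resolution of that adverse event or determination that the subject's condition is stable". Protocol 8.2 ends safety surveillance at the last of several stopping points, which include "the subject/investigator concludes his participation into the clinical study or the subject withdrawal from the clinical study". Protocol 6.3 exempts withdrawn subjects from the 5-year visit before data lock.

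**Analysis.** SAP 2.2.3 censors subjects without an event at the last time they are known to be free of it, for every time-to-event variable alike. SAP 2.2.4 counts explant as one of the possible last-contact dates for annualized rates. SAP 2.9 plans no imputation.

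**The concern.** The endpoint runs to 5 years, but collection of deaths can stop at explant. A subject withdrawn at explant would be censored for mortality from about that date, and nothing readable obliges the site to find out whether the subject is alive later. Censoring at explant is harmless only if the later risk of death matches that of subjects who keep the valve. If it is higher, 5-year freedom from death is overstated, and the data needed to check are the data not collected.

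Because withdrawal at explant is neither ordered nor ruled out, sites may differ: one may withdraw the subject and another may keep the annual visits with death collection (Protocol 5.4.4). Appendix B counts death due to reoperation as valve-related, so later deaths of that kind could be missed too.

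**Working it through.** **1. What the text covers.** There is no stated figure to reproduce: the sample-size basis is redacted and SAP 2.3 rules out hypothesis testing.

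- *Deaths in or soon after the explant operation:* expected to be captured, through follow-up of the adverse event (5.8), records of the later course (8.2) and the Death Form (8.2.1).
- *Deaths after that, if the subject stays in the study:* captured at annual follow-up (5.4.4).
- *Deaths after that, if the subject is withdrawn:* no readable requirement to look for them.
- *Valve-in-valve:* leaves the study valve in place and is not a listed withdrawal reason, so the gap concerns surgical explant.

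**2. Inputs.** From the documents: N = 350 and a 5-year horizon. All else is assumed. Central case: 5% explanted by 5 years in the absence of death; operative death m = 10%, taken as captured; later death hazard HR = 2 times background; background 5-year mortality 20%; every explanted subject withdrawn.

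**3. Model with constant hazards.**

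- Background death hazard: μ = -ln(0.80)/5 = 0.04463 per year.
- Explant hazard: ε = -ln(0.95)/5 = 0.01026 per year.
- Alive with valve in place at 5 years: 0.80 × 0.95 = 0.7600.
- Explanted: ε/(μ+ε) × (1 - 0.76) = 0.0449, or 15.7 of 350. Of these, 1.57 die at operation and 14.1 survive it.
- Explanted and alive at 5 years: the integral from 0 to 5 of ε·exp(-(μ+ε)t)·(1-m)·exp(-HR·μ·(5-t)) dt = 0.0322.
- True survival: 0.7600 + 0.0322 = 0.7922.
- Reported Kaplan-Meier, censoring operative survivors at explant: exp(-5(μ + mε)) = 0.80 × 0.95^0.1 = 0.7959.
- Shift: 0.7959 - 0.7922 = +0.37 points. Later deaths not counted: 350 × (0.0449 × 0.9 - 0.0322), about 2.85.

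**4. Sensitivity (shift in percentage points).**

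| Change from central case | Shift |
|---|---|
| HR 1 / 1.5 / 2 / 3 | -0.01 / +0.19 / +0.37 / +0.69 |
| Share withdrawn 25 / 50 / 75 / 100% | +0.09 / +0.18 / +0.27 / +0.37 |

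The central shift is zero at HR 1.02. This is slightly above 1 because subjects who have survived explant no longer face a first explant operation.

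A grid of explanted 2, 5, 8, 10%; operative death 5, 10, 15, 20%; HR 1, 1.5, 2, 3; and background mortality 10, 20, 30% gives 192 combinations. The shift runs from -0.08 to +1.91, median 0.22; 74% are below 0.5 and 92% below 1.0. The 25% at or below zero all have HR 1. With an explant hazard that rises linearly over time, the range is -0.08 to +1.34. A simpler version without a separate operative death, and with HR up to 4, reaches +2.2 at 10% explanted and 80% background survival.

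**5. Scale.** The 95% half-width, ignoring censoring, is 1.96 × √(0.2 × 0.8/350) = 4.19 points. The largest grid shift is about 0.4 of its own half-width.

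**6. Effect of longer contact on the SAP.** A subject kept in yearly contact has both an explant date and later contact dates. SAP 2.2.4 does not say which ends patient time. Under SAP 2.2.3, a subject explanted for a reason other than SVD could be read as SVD-free at each later call, which would keep someone without the study valve in the SVD risk set.

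**The case against.** A reader might infer that explanted subjects must leave the study and that their deaths are lost. The documents do not support that. Section 5.8 lists explant as a reason, does not order withdrawal, and asks for efforts at retention. SAP 3.3 does not name explant among its early-termination reasons, though that list is open-ended. Protocol 8.2.1 asks for all subject deaths to be documented, with no time limit in that sentence. These points stand, and they limit the concern to sites that do withdraw. They do not close it: 8.2.1 turns on the site becoming aware of a death, a general retention effort is not a vital-status rule, and SAP 2.2.4 suggests that contact may end at explant.

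A rule could also sit where the text cannot be read: the redactions in Protocol 6.1.1 and 6.1.2, SAP 2.1 (no text shown), the Figure 1 flow chart, or the case report form. That stands, so the claim is about readable text only.

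Censoring at the last event-free time is standard, and the gap lies in collection. But it does not follow that the SAP can stay as it is once explanted subjects are followed for longer (step 6).

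Finally, the effect is small and the endpoint is descriptive. This is conceded.

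**Conclusion.** The point holds as a cheap improvement, with medium confidence. Where a site withdraws an explanted subject, deaths after the explant episode may not be collected for 5-year all-cause mortality, and possibly not for valve-related mortality.

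In the central case the overstatement is +0.4 points (about 3 uncounted deaths in 350). It is about half that if half of explanted subjects are withdrawn, near zero at equal hazards, and -0.1 to +1.9 points over the main grid. Every rate behind these figures is assumed.

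Two stronger readings are not supported. One is that the mortality result is shown to favour the device: the direction depends on the hazard after explant, which the documents do not give. The other is that the primary endpoint is compromised: an explant that is a valve replacement is itself the primary event.

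**What to change.** **Protocol 5.8.** State that explant ends study-valve assessments only, and that explanted subjects stay in yearly vital-status and cause-of-death contact, by telephone or records, through 5 years where consent allows, with deaths sent to the CEC. Section 5.4.4 says "follow-up may occur via a telephone call with the subject for years 1, 2 and 4", so remote contact at years 3 and 5 must be allowed for these subjects.

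**Protocol 5.8 and 8.2.** Reconcile when follow-up stops. Section 8.2 says "Adverse events will be monitored until they are adequately resolved or the subject has ended his/her participation in the trial, whichever comes first", but also asks for records "until the event stabilizes and the overall clinical outcome has been ascertained", and 5.8 carries some withdrawn subjects on until their event resolves or they are stable.

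**SAP 2.2.3 and 2.2.4.** Add one or two sentences: mortality endpoints use follow-up through 5 years regardless of explant; for SVD and SVD-related reintervention, subjects without the event by explant are censored there; valve-related patient time stops at explant.

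**Subjects already withdrawn at explant.** Seek vital status where consent allows, and report how many could not be traced.

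**Cost.** A yearly call or records check for about 5 to 32 explant survivors of 350 under the assumed 2-10% explant range (5.9 × 0.80 = 4.7 to 33.3 × 0.95 = 31.6; about 14 in the central case), possibly new consent wording, and the SAP sentences. No added procedures.

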### 5.9 Echocardiographic Core Laboratory

Echocardiographic examinations at Pre-Discharge, 6 months, 3 years and 5 years will be forwarded to an echocardiographic core laboratory for interpretation. However, it is the responsibility of each site to perform the local interpretation of the echocardiogram for clinical assessment.

## Clinical Investigation Plan

The echocardiographic core laboratory will provide interpretation and documentation of each echocardiogram submitted to the Sponsor. Data obtained from the core laboratory readings will be used for study purposes only and not for clinical treatment of the subject.

Service details are outlined in the Service Agreement.

### 5.10 Study Committees

#### 5.10.1 Steering Committee (SC)

A Steering Committee will advise the Sponsor on key aspects related to the development, execution, analysis and reporting, and overall conduct of the clinical study. A Steering Committee charter will define membership of the committee and outline the purpose, roles, responsibilities, and general rules of operation for the Steering Committee. This charter is maintained by the Sponsor and sets forth the procedures for the implementation of the Steering Committee.

#### 5.10.2 Clinical Events Committee (CEC)

An independent CEC will be established for the study to provide review and adjudication of pre-defined clinical events (e.g. Edmunds Criteria events). The primary function, responsibilities and membership of the CEC will be described in detail in a CEC charter.

## 6 Statistical Considerations

### 6.1 Endpoints

#### 6.1.1 Primary Endpoint

The primary endpoint is freedom from surgical valve replacement or transcatheter valve-in-valve implantation at 5 years post implant.

##### 6.1.1.1 Analysis Methodology

Kaplan-Meier (KM) estimate and 95% confidence interval will be reported for the freedom from surgical valve replacement or transcatheter valve-in-valve implantation at 5 years post implant.

[REDACTED]

##### 6.1.1.2 Analysis Population

[REDACTED]

#### 6.1.2 Descriptive Endpoints

##### Freedom from all-cause mortality at 5 years post implant

Kaplan-Meier (KM) estimate and 95% confidence interval will be reported for the freedom from all-cause mortality at 5 years post implant. [REDACTED]

[REDACTED]

##### Freedom from valve related mortality at 5 years post implant

Kaplan-Meier (KM) estimate and 95% confidence interval will be reported for the freedom from valve related mortality at 5 years post implant. [REDACTED]

[REDACTED]

## Clinical Investigation Plan

Freedom from structural valve deterioration (SVD) at 5 years post implant

Kaplan-Meier (KM) estimate and 95% confidence interval will be reported for the freedom from SVD at 5 years post implant. [REDACTED]

Freedom from reoperation due to structural valve deterioration (SVD) at 5 years post implant

Kaplan-Meier (KM) estimate and 95% confidence interval will be reported for the freedom from reoperation due to SVD at 5 years post implant. [REDACTED]

Valve hemodynamic performance at pre-discharge, 6 months, 3 years and 5 years post implant

Left ventricular ejection fraction, mean gradient, peak gradient and effective orifice area (EOA), as assessed by the echocardiographic core laboratory, will be summarized using descriptive statistics including mean, standard deviation, median, and range. Aortic insufficiency will be summarized by frequency and percentage. [REDACTED]

### 6.2 Sample Size

The sample size of 350 is based on [REDACTED]

### 6.3 Timing of Analysis

The analyses for final report will be conducted on datasets locked after all enrolled subjects have had the 5-year study visit (excepting deaths, withdrawals and loss-to-follow-up before 5 years) or crossed the 5-year visit window without a visit (missed visit).

### 6.4 Success Criteria

The study has one primary endpoint without formal hypothesis. The primary endpoint result will be compared with data reported in the literature.

### 6.5 Interim Analysis

No interim analyses are planned for this study.

### 6.6 Statistical Criteria for Termination

There are no pre-specified criteria for terminating the clinical study on statistical grounds.

### 6.7 Deviations from Statistical Plan

There is no plan to deviate from this analysis plan. If such a deviation occurs it will be described in the clinical study report.

## 7 Risks and Benefits

Risks associated with the Trifecta GT valve have been estimated in accordance with ISO 14971: Risk Management for Medical Device, prior to conducting a clinical study. The risk analysis includes or refers

## Clinical Investigation Plan

to an objective review of published and available unpublished medical and scientific data. The risk management review of surveillance and monitoring activities finds that the Trifecta family of valves, accessories, and components/materials are safe for their intended use and that all identified residual risks associated with their use are outweighed by the benefits.

### 7.1 Risks Associated with the Devices Used in this Study

#### 7.1.1 Anticipated Adverse Device Effects

The following is a list of anticipated adverse device effects:

- angina
- cardiac arrhythmias
- endocarditis
- heart failure
- hemolysis
- hemolytic anemia
- hemorrhage
- leak, transvalvular or paravalvular
- myocardial infarction
- nonstructural dysfunction (entrapment by pannus or suture, inappropriate sizing or positioning or other)
- prosthesis regurgitation
- stroke
- structural deterioration (calcification, leaflet tear or other)
- thromboembolism
- valve thrombosis

#### 7.1.2 Risks Associated with Clinical Study Assessments

The follow up procedures required for the clinical study are considered within the scope of the standard of care for subjects undergoing aortic valve replacement, such that there is no added risk for participation in the study.

### 7.2 Risk Control Measures

Every possible effort will be taken to minimize the risks, including:

- Careful selection of experienced Investigators for the clinical study
- Adequate monitoring for each clinical study site
- Conducting the clinical study in accordance with the CIP, all applicable laws and regulations and any conditions of approval imposed by the appropriate IRB/EC or applicable regulatory authorities where the clinical study is performed
- Preparation of the Trifecta GT valve device and performance of the implantation procedure in accordance with the device IFUs
- Training of Investigators both on the CIP and Trifecta GT implantation procedure.

### 7.3 Possible interactions with concomitant treatments

The Trifecta GT valve has magnetic resonance conditions and any use of MRI in implanted subjects should be done according to the current Instructions for Use (IFU).

